9.3.1. Solicited Events and Symptoms

Systemic solicited adverse events were collected pre-vaccination, and systemic and local solicited adverse events were collected 30 minutes post-vaccination and then daily for 7 days after the vaccination and graded on a scale of 0 (absent), 1 (mild), 2 (moderate) and 3 (severe). Systemic events include: fatigue, headache, myalgia, arthralgia, nausea, chills and fever. Local events include: pain at injection site, erythema, and induration.

For each systemic and local event, any systemic event, any local event, and any solicited event, the maximum severity over 7 days after the third vaccination will be summarized for the Safety population. The number and percentage of subjects reporting each event will be summarized by the maximum severity and treatment group (Table 389). For each event the denominator is the number of subjects with non-missing data for the specific event.

The number of subjects reporting a solicited adverse event will be summarized for each day post-vaccination both in a summary table (starting with Table 390 and ending with Table 407) and graphically in a bar chart (Figure 1250, Figure 1251, Figure 1252, Figure 1253, Figure 1254, and Figure 1255).

The mean, standard deviation, median, minimum and maximum duration of solicited events will be summarized (Table 408).

Day of solicited symptom onset will be summarized graphically (Figure 1256, Figure 1257, Figure 1258, Figure 1259, Figure 1260, and Figure 1261).

Solicited adverse events by subject will be presented in listings (Listing 10 and Listing 11) and graphically (starting with Figure 1262 and ending with Figure 1275).

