3. STUDY OBJECTIVES AND ENDPOINTS

3.1. Study Objectives and Endpoints

| OBJECTIVES | ENDPOINTS (OUTCOME MEASURES) |
|--|--|
| Primary | |
| 
 To evaluate the safety and reactogenicity of mRNA-1273 and mRNA-1273.351 vaccines, in naïve individuals. | 
 Frequency and grade of each solicited local and systemic reactogenicity AE during a 7-day follow-up period post each vaccination. Frequency and grade of any unsolicited AEs during the 28-day follow-up period post each vaccination. Frequency of any SAEs, Protocol Specified AESIs, NOCMCs, and MAAEs from the first vaccination through 12 months after the last vaccination. |
| Secondary | |
| 
 To assess humoral immunogenicity of mRNA-1273 and mRNA-1273.351 vaccines, in naïve individuals. | 
 Response rate, and magnitude of SARS-CoV-2-specific antibody binding and neutralization titers in serum samples as assessed via a range of assays at all timepoints. |
| Exploratory | |
| 
 To assess, in at least a subset of samples the innate immune response and B cell response following vaccination. | 
 Magnitude, phenotype, and percentage of innate immune cells and SARS-CoV-2 specific B cells, as measured by flow cytometry, and targeted B cell repertoire analysis at different timepoints post vaccination relative to baseline. |
| 
 To assess, in at least a subset of samples, the SARS-CoV-2 S protein-specific T cell responses. | 
 Magnitude, phenotype, and percentage of cytokine producing S protein-specific T cells, as measured by flow cytometry at different timepoints post vaccination relative to baseline. |

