4.4.6. Treatment Compliance

All subjects are to receive 2 (Arms 2C-H) or 3 (Arms 2A-B) doses of study product administered in the clinic. The number of doses received will be reported in [Table 7](#) (Arms 2A-B) and [Table 8](#) (Arms 2C-H).

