9. SAFETY EVALUATION

Summaries and analysis of safety data will be presented for the Safety Analysis Population.

Solicited AEs will be summarized by severity for each day post vaccination (Days 1-8) for each dose and as the maximum severity over all 8 days. Additionally, solicited AEs will be analyzed by taking the most severe response over the follow-up period and using standard techniques, such as exact confidence intervals (CI), to summarize the proportion of subjects reporting each symptom, any local symptom, and any systemic symptom.

Unsolicited non-serious AEs will be collected from the time of the first vaccination through 28 days after the final vaccination. Unsolicited AEs will be coded by MedDRA for preferred term and system organ class (SOC). SAEs, Protocol Specified AESIs, MAAEs, and NOCMCs will be collected from the time of first vaccination through 12 months after the final vaccination. The numbers of SAEs and MAAEs will be reported by detailed listings showing the event description, MedDRA preferred term and SOC, relevant dates (vaccinations and AEs), severity, relatedness, and outcome for each event. Non-serious unsolicited AEs will be summarized as number and percentage of subjects reporting at least one event in each MedDRA preferred term and SOC, cross tabulated by severity and relationship to study product. Additionally, the proportion of subjects and exact 95% CIs of AEs in aggregate and by MedDRA categories will be computed.

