| Headache | None | | | | | | | | | | | | | | | | | | |
| | Mild | | | | | | | | | | | | | | | | | | |
| | Moderate | | | | | | | | | | | | | | | | | | |
| | Severe | | | | | | | | | | | | | | | | | | |
| Myalgia | None | | | | | | | | | | | | | | | | | | |
| | Mild | | | | | | | | | | | | | | | | | | |
| | Moderate | | | | | | | | | | | | | | | | | | |
| | Severe | | | | | | | | | | | | | | | | | | |
| Nausea | None | | | | | | | | | | | | | | | | | | |
| | Mild | | | | | | | | | | | | | | | | | | |
| | Moderate | | | | | | | | | | | | | | | | | | |
| | Severe | | | | | | | | | | | | | | | | | | |
| Any Local Symptom | None | | | | | | | | | | | | | | | | | | |
| | Mild | | | | | | | | | | | | | | | | | | |
| | Moderate | | | | | | | | | | | | | | | | | | |
| | Severe | | | | | | | | | | | | | | | | | | |
| Erythema/Redness | None | | | | | | | | | | | | | | | | | | |
| | Mild | | | | | | | | | | | | | | | | | | |

| | | Arm 2A (N=X) | | Arm 2B (N=X) | | Arm 2C (N=X) | | Arm 2D (N=X) | | Arm 2E (N=X) | | Arm 2F (N=X) | | Arm 2G (N=X) | | Arm 2H (N=X) | | All Subjects (N=X) | |
|---|----------|-----------------|---|-----------------|---|-----------------|---|-----------------|---|-----------------|---|-----------------|---|-----------------|---|-----------------|---|--------------------------|---|
| Symptom | Severity | n | % | n | % | n | % | n | % | n | % | n | % | n | % | n | % | n | % |
| | Moderate | | | | | | | | | | | | | | | | | | |
| | Severe | | | | | | | | | | | | | | | | | | |
| Erythema/Redness Measurement (mm) | None | | | | | | | | | | | | | | | | | | |
| | Mild | | | | | | | | | | | | | | | | | | |
| | Moderate | | | | | | | | | | | | | | | | | | |
| | Severe | | | | | | | | | | | | | | | | | | |
| Induration/Swelling | None | | | | | | | | | | | | | | | | | | |
| | Mild | | | | | | | | | | | | | | | | | | |
| | Moderate | | | | | | | | | | | | | | | | | | |
| | Severe | | | | | | | | | | | | | | | | | | |
| Induration/Swelling Measurement (mm) | None | | | | | | | | | | | | | | | | | | |
| | Mild | | | | | | | | | | | | | | | | | | |
| | Moderate | | | | | | | | | | | | | | | | | | |
| | Severe | | | | | | | | | | | | | | | | | | |
| Pain | None | | | | | | | | | | | | | | | | | | |
| | Mild | | | | | | | | | | | | | | | | | | |
| | Moderate | | | | | | | | | | | | | | | | | | |
| | Severe | | | | | | | | | | | | | | | | | | |

Severity is the maximum severity reported over all solicited symptoms post dosing for each subject.

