N=All subjects receiving vaccination with any solicited event data recorded in the database.

Table 390: Summary of Solicited Events by Days Post Dose 1, Symptom, and Treatment Group – Treatment Arm 2A (Three Vaccinations)

| | | Pre-Dose (N=X) | | Post-Dose (N=X) | | Day 1 (N=X) | | Day 2 (N=X) | | Day 3 (N=X) | | Day 4 (N=X) | | Day 5 (N=X) | | Day 6 (N=X) | | Day 7 (N=X) | | Day 8+ ¹ (N=X) | | Any Post-Dose ² | |
|----------------------|----------|-------------------|---|--------------------|---|----------------|---|----------------|---|----------------|---|----------------|---|----------------|---|----------------|---|----------------|---|------------------------------|---|-------------------------------|---|
| Symptom | Severity | n | % | n | % | n | % | n | % | n | % | n | % | n | % | n | % | n | % | n | % | n | % |
| Any Symptom | None | | | | | | | | | | | | | | | | | | | | | | |
| | Mild | | | | | | | | | | | | | | | | | | | | | | |
| | Moderate | | | | | | | | | | | | | | | | | | | | | | |
| | Severe | | | | | | | | | | | | | | | | | | | | | | |
| Any Systemic Symptom | None | | | | | | | | | | | | | | | | | | | | | | |
| | Mild | | | | | | | | | | | | | | | | | | | | | | |
| | Moderate | | | | | | | | | | | | | | | | | | | | | | |
| | Severe | | | | | | | | | | | | | | | | | | | | | | |
| Arthralgia | None | | | | | | | | | | | | | | | | | | | | | | |
| | Mild | | | | | | | | | | | | | | | | | | | | | | |
| | Moderate | | | | | | | | | | | | | | | | | | | | | | |
| | Severe | | | | | | | | | | | | | | | | | | | | | | |
| Fatigue | None | | | | | | | | | | | | | | | | | | | | | | |
| | Mild | | | | | | | | | | | | | | | | | | | | | | |
| | Moderate | | | | | | | | | | | | | | | | | | | | | | |
| | Severe | | | | | | | | | | | | | | | | | | | | | | |
| Fever | None | | | | | | | | | | | | | | | | | | | | | | |
| | Mild | | | | | | | | | | | | | | | | | | | | | | |
| | Moderate | | | | | | | | | | | | | | | | | | | | | | |
| | Severe | | | | | | | | | | | | | | | | | | | | | | |
| Feverishness | None | | | | | | | | | | | | | | | | | | | | | | |
| | Mild | | | | | | | | | | | | | | | | | | | | | | |

| Symptom | Severity | Pre-Dose (N=X) | | Post-Dose (N=X) | | Day 1 (N=X) | | Day 2 (N=X) | | Day 3 (N=X) | | Day 4 (N=X) | | Day 5 (N=X) | | Day 6 (N=X) | | Day 7 (N=X) | | Day 8+ ¹ (N=X) | | Any Post-Dose ² | | |

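### SAP Section 9.3.1 ties the maximum-severity summary of solicited AEs (Table 389) to the third vaccination, which 120 of 150 planned subjects are not scheduled to receive

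*SAP*

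**What the plan says.** The first-listed primary endpoint in SAP Section 3.1 is "Frequency and grade of each solicited local and systemic reactogenicity AE during a 7-day follow-up period post each vaccination".

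Section 9 (Safety Evaluation) then asks for solicited AEs to be summarised by severity on each day, "for each dose and as the maximum severity over all 8 days". It adds an analysis with exact confidence intervals based on "taking the most severe response over the follow-up period".

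Section 9.3.1, which specifies Table 389, sets a narrower window: "the maximum severity over 7 days after the third vaccination will be summarized for the Safety population". Its next sentence sends the result to Table 389 by treatment group.

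On dosing, Section 4.4.6 says "All subjects are to receive 2 (Arms 2C-H) or 3 (Arms 2A-B) doses of study product administered in the clinic". Table 1 agrees and lists no third vaccination for Arms 2C-H.

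The Table 389 shell (Appendix 1, Section 14.3.1.1) has columns for all eight arms and for all subjects. Its footnotes read "Severity is the maximum severity reported over all solicited symptoms post dosing for each subject" and "N=All subjects receiving vaccination with any solicited event data recorded in the database". Neither mentions a third dose.

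**The concern.** Section 9.3.1 gives the operative rule for one table of a primary safety endpoint, and that rule cannot be carried out for six of the eight arms that the table displays. For the two arms where it can be carried out, it discards the first two vaccinations, although the endpoint counts each one.

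The plan therefore holds several windows for the same summary: dose 3 only (Section 9.3.1), per dose or over all 8 days (Section 9), the most severe response over follow-up (Section 9), and an unspecified post-dosing period (Table 389 footnote). A programmer who follows one will contradict another. In an open-label trial it is better not to leave that choice until the reactogenicity data are in view.

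**Working it through.** **Inputs.** Arm sizes are from SAP Section 5 and Table 1: 15 in each of 2A and 2B, 20 in each of 2C to 2H. Doses per arm are from Section 4.4.6 and Table 1: three in 2A-B, two in 2C-H.

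**Reproducing the plan's total.** 2 × 15 + 6 × 20 = 30 + 120 = 150, which matches the stated Cohort 2 size.

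**Subjects inside the Section 9.3.1 window.** Scheduled for a third vaccination: 2 × 15 = 30, and 30/150 = 20%. Not scheduled for one: 6 × 20 = 120, and 120/150 = 80%.

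**Vaccinations inside the window.** All planned vaccinations: 30 × 3 + 120 × 2 = 90 + 240 = 330. Third vaccinations: 30, and 30/330 = 9.1%. The 300 left out are 60 first and second doses in Arms 2A-B and 240 doses in Arms 2C-H.

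**Effect on Table 389.** Section 9.3.1 takes as denominator the subjects with non-missing data for the event. For a dose-3 window that number is zero in each of Arms 2C to 2H, so six of the eight arm columns hold nothing. The all-subjects column would then describe Arms 2A-B alone, under a heading that names everyone.

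**The sources side by side.**

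| Source in the SAP | Window for severity | Works for all eight arms? |
|---|---|---|
| Section 3.1 | each vaccination | yes |
| Section 9 | each dose; also all 8 days; also follow-up period | yes |
| Section 9.3.1 | third vaccination only | no, 2A-B only |
| Table 389 shell and footnotes | post dosing, dose not stated | yes |

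Section 9.3.1 is the outlier. It also conflicts with itself: it names the Safety population, which Section 6.2.1 defines by receipt of one dose, not by receipt of the third.

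**Whether other tables fill the gap.** Tables 390-407 are 18 tables: 2 × 3 for Arms 2A-B plus 6 × 2 for Arms 2C-H. They show severity by day after every dose in every arm. Their Any Post-Dose column carries a footnote that lets one subject fall in several severity categories, so it is not a single-count maximum. Table 389 is the only solicited-event table that sets each subject's maximum severity side by side for all arms.

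**The case against.** The strongest reply is that nobody would produce an empty table. Section 9, the eight arm columns and both footnotes all point away from a dose-3 window, and Tables 390-407 report every dose in every arm. On that view this is a stray phrase and the primary endpoint is safe.

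Much of this stands. A reader might infer from Section 9.3.1 that maximum severity is defined only after the third vaccination, or that the per-vaccination endpoint goes unanalysed. The documents support neither: Section 9 gives a per-dose rule, and the day-by-day tables cover all 330 planned vaccinations. What does not stand is that the context settles the matter. With the phrase removed, the remaining text still permits a per-dose maximum or one maximum over all doses, and the shell has a single block that does not say which.

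A reader might also infer that the footnote prescribes a maximum pooled over doses and so makes the three-dose arms look more reactogenic. The footnote says post dosing and does not mention pooling. If it were pooled, the size of any effect could not be taken from the SAP, which gives no per-dose rate. Assuming an equal, independent risk p at each dose, the three-dose minus two-dose gap is p(1-p)²: 4.5 points at p = 5%, 14.7 at 30% and 3.2 at 80%. Positive correlation within subjects would generally shrink it. The extra dosing occasion is also a real feature of the three-dose regimen, and the summaries are descriptive. This is a reason to label such a row clearly; it does not show a biased result.

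**Conclusion.** Wrong as written. The Section 9.3.1 window contradicts Sections 3.1 and 9 and the Table 389 shell. Applied literally, it excludes 120 of 150 planned subjects and 300 of 330 planned vaccinations from Table 389. The harm is confined to that table and to the ambiguity over its window; severity by day after each dose is reported elsewhere. The counts are planned numbers: they assume full enrolment, which Section 4.1 allows to close early, and completion of all scheduled doses. The contradiction does not depend on either assumption.

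**What to change.** In Section 9.3.1, replace the reference to the third vaccination with *after each vaccination, by dose number and treatment arm*. Divide Table 389 into dose 1, dose 2 and dose 3 blocks, the last for Arms 2A-B only, and align its footnote with that window.

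If a maximum over all doses is kept as well, label it as such and note that it spans three doses in Arms 2A-B and two in Arms 2C-H. Restricting that row to doses 1 and 2 for comparability is not recommended as a default: per Table 1, the third dose is the only mRNA-1273.351 dose that Arms 2A-B receive.

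The cost is one sentence of SAP text, extra table blocks and a footnote. No new data are needed.

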9.3.2. Unsolicited Adverse Events

The proportion of subjects reporting at least one unsolicited adverse event will be summarized by MedDRA system organ class and preferred term. Denominators for percentages are the number of subjects who received the vaccination.

Adverse events by subject will be presented in Listing 12.

The following summaries for unsolicited adverse events will be presented by MedDRA system organ class, preferred term, and Treatment Group:

- Subject incidence and total frequency of adverse events ([Table 409](#));
- Summary of severity and relationship to study product ([Table 410](#) and [Table 411](#));
- Listing of Non-Serious, Unsolicited, Moderate or Severe Adverse Events ([Table 412](#));
- Bar chart of frequency of adverse events by severity and MedDRA system organ class ([Figure 1274](#));
- Bar chart of incidence of adverse events by severity and MedDRA system organ class ([Figure 1275](#)).

9.4. Deaths, Serious Adverse Events and other Significant Adverse Events

The following listings will be presented including Subject ID, Age (years) Adverse Event Description, Adverse Event Onset Date/End Date, Last Dose Received/Days Post Dose, Reason Reported as an SAE, Relationship to Treatment, Alternate Etiology if not Related, Outcome, and Duration of Event (days):

- Deaths and Serious Adverse Events ([Table 412](#));
- Adverse Events of Special Interest, New Onset Chronic Medical Conditions and Medically Attended Adverse Events ([Table 414](#)).

9.5. Pregnancies

For any subjects in the Safety population who became pregnant during the study, every attempt will be made to follow these subjects to completion of pregnancy to document the outcome, including information regarding any complications with pregnancy and/or delivery. A listing of pregnancies and outcomes will be presented ([Listing 16](#), [Listing 17](#), [Listing 18](#), [Listing 19](#), and [Listing 20](#)).

9.6. Clinical Laboratory Evaluations

Not applicable.

9.7. Vital Signs and Physical Evaluations

Vital sign measurements included systolic blood pressure, diastolic blood pressure, pulse, and oral temperature. Vital signs were assessed at Study Days 1, 15, 29, 43, 57, 71, 85, 147, 237, and 422 (Arms 2A-B) and Study Days 1, 15, 29, 43, 57, 119, 209, and 394 (Arms 2C-H). Vital signs will be tabulated by visit and Treatment Group starting with [Table 415](#) and ending with [Table 424](#) ([Listing 13](#)).

Physical Examinations were only to be performed if clinically indicated at Study Days 1, 15, 29, 43, 57, 71, 85, 147, 237, and 422 (Arms 2A-B) and Study Days 1, 15, 29, 43, 57, 119, 209, and 394 (Arms 2C-H). The following body systems will be assessed: Abdomen, Cardiovascular/heart, Extremities, General Appearance, Hepatobiliary/spleen, HEENT, Lymph nodes, Musculoskeletal, Neck, Neurological, Pulmonary/Chest, and Skin ([Listing 14](#)).

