6. GENERAL STATISTICAL CONSIDERATIONS

6.1. General Principles

In general, continuous variables will be summarized using the following descriptive statistics: n (non-missing sample size), mean, standard deviation, median, maximum, and minimum. The frequency and percentages (based on the non-missing sample size) of observed levels will be reported for all categorical measures. In general, all data will be listed, sorted by site, treatment, and subject, and when appropriate by visit number within subject. All summary tables will be structured with a column for each treatment and will be annotated with the total population size relevant to that table/cohort, including any missing observations.

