9.5.1 Efficacy/Immunogenicity and Safety Measurements Assessed and Flow Chart

Table 2: Schedule of Study Procedures for Treatment Arms 2A-B (Three Vaccinations)

| Study Day | -42 to -1 | 1 | 8* | 15 | 29 | 36* | 43 | 57 | 64* | 71 | 85 | 147 | 237 | 422 | Unsc Visit | Early Term Visit |
|--|-------------------------|----------------|----|----------------|----|-----------------|-----------------|-----------------|-----------------|-----------------|-----------------|-----------------|-----------------|-----------------|------------|------------------|
| Visit Window (±number of days) | | 0 | 1 | 2 | 2 | 1 | 2 | 2 | 1 | 2 | 2 | 7 | 7 | 14 | | |
| Study Visit | Screening (optional) 00 | 01 | 02 | 03 | 04 | 05 ^e | 06 ^e | 07 ^e | 08 ^f | 09 ^f | 10 ^f | 11 ^f | 12 ^f | 13 ^f | | |
| Informed Consent | X | X ^a | | | | | | | | | | | | | | |
| Review Eligibility Criteria | X | X | | | | | | | | | | | | | | |
| Medical History | X | X ^a | | | | | | | | | | | | | | |
| Vaccination | | X | | | X | | | X | | | | | | | | |
| Concomitant Medications | | X | X | X | X | X | X | X | X | X | X | | | | | |
| Interim History | | X ^b | | X | X | | X | X | | X | X | X | X | X | X | X |
| Symptom-Directed Physical Examination | X | X | | X | X | | X | X | | X | X | X | X | X | X | X |
| Vital Signs ^c | | X | | X | X | | X | X | | X | X | X | X | X | X | X |
| Height and Weight (for BMI) | X | X ^a | | | | | | | | | | | | | | |
| Pregnancy Test ^d | | X | | | X | | | X | | | | | | | | |
| Memory Aid: Solicited AEs | | X | X | X ^g | X | X | X ^g | X | X | X ^g | | | | | | |
| Unsolicited AEs | | X | X | X | X | X | X | X | X | X | X | | | | | |
| SAEs, Protocol Specified AESIs, MAAEs, and NOCMCs | | X | X | X | X | X | X | X | X | X | X | X | X | X | X | X |
| Serum for Serological Immunogenicity Assays | | X | | X | X | | X | X | | X | X | X | X | X | | X |
| Peripheral Blood Mononuclear Cells (PBMCs) for Cellular Immunology Assays (and Plasma) | | X | | X | X | | X | X | | X | | | X | X | | X |

* Telephone call.

- a) If not performed at Visit 00.
- b) If medical history performed at Visit 00, then interim history at Visit 01.
- c) Vital signs to be obtained pre and post vaccination. Otherwise, only as clinically indicated.
- d) For women of childbearing potential, a negative urine pregnancy test on Day 1 with results confirmed prior to enrollment.
- e) Visits 05-07 windows should be based off the actual Visit 04 date.

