- f) Visits 08-13 windows should be based off the actual Visit 07 date.
- g) Collect Memory Aid and assess for delayed onset local reactions.

Table 3: Schedule of Study Procedures for Treatment Arms 2C-H (Two Vaccinations)

| Study Day | -42 to -1 | 1 | 8* | 15 | 29 | 36* | 43 | 57 | 119 | 209 | 394 | Unsc Visit | Early Term Visit |
|--|-------------------------|----------------|----|----------------|----|-----------------|-----------------|-----------------|-----------------|-----------------|-----------------|------------|------------------|
| Visit Window (±number of days) | | 0 | 1 | 2 | 2 | 1 | 2 | 2 | 7 | 7 | 14 | | |
| Study Visit | Screening (optional) 00 | 01 | 02 | 03 | 04 | 05 ^e | 06 ^e | 07 ^e | 08 ^e | 09 ^e | 10 ^e | | |
| Informed Consent | X | X ^a | | | | | | | | | | | |
| Review Eligibility Criteria | X | X | | | | | | | | | | | |
| Medical History | X | X ^a | | | | | | | | | | | |
| Vaccination | | X | | | X | | | | | | | | |
| Concomitant Medications | | X | X | X | X | X | X | X | | | | | |
| Interim History | | X ^b | | X | X | | X | X | X | X | X | X | X |
| Symptom-Directed Physical Examination | X | X | | X | X | | X | X | X | X | X | X | X |
| Vital Signs ^c | | X | | X | X | | X | X | X | X | X | X | X |
| Height and Weight (for BMI) | X | X ^a | | | | | | | | | | | |
| Pregnancy Test ^d | | X | | | X | | | | | | | | |
| Memory Aid: Solicited AEs | | X | X | X ^f | X | X | X ^f | | | | | | |
| Unsolicited AEs | | X | X | X | X | X | X | X | | | | | |
| SAEs, Protocol Specified AESIs, MAAEs, and NOCMCs | | X | X | X | X | X | X | X | X | X | X | X | X |
| Serum for Serological Immunogenicity Assays | | X | | X | X | | X | X | X | X | X | | X |
| Peripheral Blood Mononuclear Cells (PBMCs) for Cellular Immunology Assays (and Plasma) | | X | | X | X | | X | | | X | X | | X |

* Telephone call.

- a) If not performed at Visit 00.
- b) If medical history performed at Visit 00, then interim history at Visit 01.
- c) Vital signs to be obtained pre and post vaccination. Otherwise, only as clinically indicated.
- d) For women of childbearing potential, a negative urine pregnancy test on Day 1 with results confirmed prior to enrollment.
- e) Visits 05-10 windows should be based off the actual Visit 04 date.
- f) Collect Memory Aid and assess for delayed onset local reactions.

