14.3.6 Displays of Vital Signs

Table 415: Vital Signs by Assessment, Maximum Severity, Time Point, and Treatment Group, Any Assessment – All Subjects, Treatment Arms 2A-B (Three Vaccinations)

| | | Arm 2A (N=X) | | Arm 2B (N=X) | | All Subjects (N=X) | |
|------------|----------|-----------------|---|-----------------|---|-----------------------|---|
| Time Point | Severity | n | % | n | % | n | % |
| Baseline | None | | | | | | |
| | Mild | | | | | | |
| | Moderate | | | | | | |
| | Severe | | | | | | |
| Day 15 | None | | | | | | |
| | Mild | | | | | | |
| | Moderate | | | | | | |
| | Severe | | | | | | |
| Day 29 | None | | | | | | |
| | Mild | | | | | | |
| | Moderate | | | | | | |
| | Severe | | | | | | |
| Day 43 | None | | | | | | |
| | Mild | | | | | | |
| | Moderate | | | | | | |
| | Severe | | | | | | |
| Day 57 | None | | | | | | |
| | Mild | | | | | | |
| | Moderate | | | | | | |
| | Severe | | | | | | |

| | | Arm 2A (N=X) | | Arm 2B (N=X) | | All Subjects (N=X) | |
|-------------------------------|----------|-----------------|---|-----------------|---|-----------------------|---|
| Time Point | Severity | n | % | n | % | n | % |
| Day 71 | None | | | | | | |
| | Mild | | | | | | |
| | Moderate | | | | | | |
| | Severe | | | | | | |
| Day 85 | None | | | | | | |
| | Mild | | | | | | |
| | Moderate | | | | | | |
| | Severe | | | | | | |
| Day 147 | None | | | | | | |
| | Mild | | | | | | |
| | Moderate | | | | | | |
| | Severe | | | | | | |
| Day 237 | None | | | | | | |
| | Mild | | | | | | |
| | Moderate | | | | | | |
| | Severe | | | | | | |
| Day 422 | None | | | | | | |
| | Mild | | | | | | |
| | Moderate | | | | | | |
| | Severe | | | | | | |
| Max Severity Post Baseline | None | | | | | | |
| | Mild | | | | | | |
| | Moderate | | | | | | |

| | | Arm 2A (N=X) | | Arm 2B (N=X) | | All Subjects (N=X) | |
|------------|----------|-----------------|---|-----------------|---|-----------------------|---|
| Time Point | Severity | n | % | n | % | n | % |
| | Severe | | | | | | |

Note: The “Max Post Baseline” rows indicate the maximum severity experienced by each subject at any time point post baseline, including unscheduled assessments.
N = Number of subjects in the Safety Population.

Tables with Similar Format:

- Table 416: Vital Signs by Assessment, Maximum Severity, Time Point, and Treatment Group, Systolic Blood Pressure – All Subjects, Treatment Arms 2A-B (Three Vaccinations)**

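### Section 9.7 presents vital signs as measured at every clinic visit, while footnote c of the schedules plans them only around vaccination and otherwise when clinically indicated, so most by-visit percentages may describe a selected group

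*SAP*

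**What the plan says.** Section 9.7 gives the vital-sign days without any condition. For the three-dose arms: "Vital signs were assessed at Study Days 1, 15, 29, 43, 57, 71, 85, 147, 237, and 422 (Arms 2A-B". For the two-dose arms: "Study Days 1, 15, 29, 43, 57, 119, 209, and 394 (Arms 2C-H). Vital signs will be tabulated by visit and Treatment Group". The next paragraph of the same section does attach a condition to physical examinations on the same days: "Physical Examinations were only to be performed if clinically indicated at Study Days 1, 15, 29, 43, 57, 71, 85, 147, 237, and 422".

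Tables 2 and 3 mark vital signs at those same clinic visits, but the row carries footnote c in both tables: "Vital signs to be obtained pre and post vaccination. Otherwise, only as clinically indicated". Vaccination falls on Days 1, 29 and 57 in Arms 2A-B and on Days 1 and 29 in Arms 2C-H.

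Tables 415 to 424 give each visit a block of None, Mild, Moderate and Severe with n and %. The table note reads "N = Number of subjects in the Safety Population". The rows run from Baseline straight to Day 15 and end with a row for maximum severity post baseline, which also takes in unscheduled assessments. Section 6.1 sets the percentage rule: "The frequency and percentages (based on the non-missing sample size) of observed levels will be reported for all categorical measures". Section 3.2 defines baseline as the Day 1 value before the first vaccination.

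**The concern.** The text of 9.7 and footnote c describe two different data sets. Under the text, every subject who attends has a reading at every clinic visit, and a by-visit severity percentage is a property of the arm. Under the footnote, most visits contribute readings only from subjects whom someone chose to measure. A percentage of abnormal grades among those subjects reflects the reason for measuring them as much as the vaccine, yet the shell would present it in the same form as a routine assessment.

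The readings that the footnote does plan for everyone, just before and just after each injection, are the ones the shells show least clearly. The Day 1 post-dose reading has no row, and the single row for Day 29 (and for Day 57 in Arms 2A-B) does not say whether it is the pre-dose value, the post-dose value or the worse of the two. At stake is whether a reader can see acute changes after each dose, and whether the later rows can be read as rates at all.

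**Working it through.** The plan states no figure on this point, so there is none to reproduce. The check is a count of shell rows against vaccination days, followed by an illustration.

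**Inputs.** Visit days from Section 9.7; vaccination days and footnote c from Tables 2 and 3; row structure from the shells of Tables 415 and 420; denominator from Section 6.1; arm sizes of 15 (2A, 2B) and 20 (2C to 2H) from Section 5.

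**Visit rows without a planned reading, if footnote c governs.**

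| | Arms 2A-B (Table 415) | Arms 2C-H (Table 420) |
|---|---|---|
| Visit rows, counting Baseline as Day 1 | 10 | 8 |
| Vaccination days | 1, 29, 57 (3) | 1, 29 (2) |
| Rows with no planned reading | 10 − 3 = 7 | 8 − 2 = 6 |
| Those days | 15, 43, 71, 85, 147, 237, 422 | 15, 43, 57, 119, 209, 394 |
| As a share of post-baseline visit rows | 7 of 9 | 6 of 7 |

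These counts leave out the closing maximum-severity row, which is not a visit.

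**Planned readings against rows provided.** With one reading before and one after each dose, Arms 2A-B have 2 × 3 = 6 planned readings per subject and Arms 2C-H have 2 × 2 = 4. The shells give 3 and 2 rows for those days.

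**What selection does to a percentage.** Under Section 6.1, % = 100 × (subjects at that grade) / (subjects measured). The SAP does not say how many subjects would be measured at an unplanned visit, so the number is assumed over a range. For one abnormal reading:

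| Subjects measured | 1 | 3 | 5 | 10 | whole arm of 15 | whole arm of 20 |
|---|---|---|---|---|---|---|
| % abnormal | 100 | 33.3 | 20 | 10 | 6.7 | 5.0 |

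The same event can be printed as anything from 5% to 100%, depending on how many other subjects happened to be measured. Nothing in the shell tells the reader that measurement was selective.

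**The case against.** The strongest reply is that the defect is one missing qualifier. The days in 9.7 match the clinic visits marked in Tables 2 and 3, so no schedule was invented. The four grade counts in each block add up to the number measured, so a careful reader can recover it. Both points are fair, and they limit the weight of the finding. They do not remove the contradiction or make the percentages comparable across rows.

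Three stronger readings are tempting, and the document does not support them.

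- A reader might infer that percentages will be diluted by dividing by the whole Safety Population, because that is the N printed on the tables. Section 6.1 sets the non-missing denominator and separately says that tables are annotated with the total population size. The printed N is best read as that annotation. The total-population rule in Section 9.3 concerns incidence of adverse events and does not displace 6.1 for these by-visit grades.
- A reader might infer that the Day 1 post-dose reading is lost. Because baseline is the pre-vaccination value, that reading enters the maximum post-baseline row, and individual values go to Listing 13. It is hidden within a summary rather than dropped.
- A reader might infer that a post-dose abnormality on Day 29 or 57 would disappear. The table titles refer to maximum severity, so the row plausibly shows the worst grade at that visit. What is lost is whether that grade came before or after the injection.

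**Conclusion.** Section 9.7 and footnote c contradict each other on when vital signs are taken, and the shells follow 9.7. The document does not settle which statement describes the data collected; that is for the sponsor. If the footnote governs, 7 of 10 visit rows in Table 415 and 6 of 8 in Table 420, and the same rows in the tables of similar format through 424, give percentages for clinically selected subjects. The planned pre-dose and post-dose readings then cannot be told apart by dose. If 9.7 governs, the selection problem falls away and the footnote is what needs changing.

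The effect is on a descriptive safety display. Vital signs are not among the endpoints named in Section 3.1, and nothing in the SAP makes a decision depend on these tables. It is still worth correcting: safety is the primary objective, and readings around each injection are the planned part of this assessment under the footnote. The size of any distortion depends on how many subjects were measured at the other visits, which the SAP does not state.

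**What to change.** 1. Reconcile Section 9.7 with footnote c of Tables 2 and 3, so that one statement says when vital signs are planned and when they are taken only for cause.
2. In Tables 415 to 424, give separate pre-dose and post-dose rows at each vaccination visit (Days 1 and 29, plus Day 57 for Arms 2A-B), with the number measured shown as the denominator. That is six rows for Arms 2A-B and four for Arms 2C-H. The solicited-event shell, Table 390, already separates pre-dose from post-dose and provides for a not-reported row.
3. If footnote c governs, show counts with the number measured at the other visits, or list the readings. Do not print by-visit percentages as though all subjects had been assessed.
4. Keep those readings in the maximum post-baseline row, which is meant to include unscheduled assessments. Moving them to a listing alone would take readings made for clinical reasons out of the summary.

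The cost is a sentence in 9.7 or the footnote and edits to the shells. No new data should be needed, provided the database holds pre-dose and post-dose readings separately; footnote c implies that both are taken, but the SAP does not show how they are stored.
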